Events that are ongoing at the time a participant completes or leaves the study should be left open for stop dates (i.e. report as 'ongoing'). The participant should be probed for any stop dates that are now known to close out previously recorded events. All adverse event report forms will be reviewed quarterly (or sooner as necessary) per the Data Safety Monitoring Plan below and reported as indicated.

Data Safety Monitoring Plan:

Adverse events will be reviewed every 3 months as needed by the study team physicians ([name], [name], [name]) and study coordinators. In case of uncertainty or disagreements among the above individuals regarding adjudication of possible study-related AES, or serious AEs, the team will seek additional input from non-study clinicians (e.g. [name] of the Pulmonary Division)

Potential Benefits Gained from Data

The described risks of the study represent minor increases over minimal risk. Spirometry and sputum induction are used in clinical care setting, where the incidence of serious adverse events related to these procedures is very low. The anticipated scientific benefits of this study are increased knowledge of the biological effects of dupilumab on host-microbiome interactions, how such effects may impact clinical responses to the treatment and identify potential new mechanisms. We believe the potential benefits of the study outweigh the minor increase over minimal risk of the proposed testing procedures.

X. Sample Processing/Analysis (Overview). Respiratory samples will be processed for microbiota analysis by 16S rRNA and shotgun DNA sequencing, measurement of airway bacterial burden by quantitative PCR, cytokine measurements, sputum inflammatory cell counts/differential and airway gene expression studies (targeted). Blood will be analyzed for complete blood count with differential analysis, total IgE, respiratory allergen specific IgE, and blood cytokine mediators. Stool will be processed for gut microbiome and metabolomic analyses (global and targeted for short chain fatty acids). These data will be generated using University of Michigan Clinical Lab and Research Core facilities (Microbiome Core, Advanced Genomics Core, Metabolomics Core), as well as subcontract collaboration with UNC-Chapel Hill (Spirovation).

XI. Data Management and Analysis.

A HIPAA-compliant, passcode-secured REDCAP database for the study will be created. The study team (coordinator, PI) will enter all clinical test results. This database will reside on University of Michigan servers approved to store HIPAA-related research information. Access is given only to study-specific research team members for whom the PI provides permission. Subjects will be assigned a code using a study-specific identifier for downstream sample processing and data analyses. All samples for molecular sequencing/cytokine analysis will be identified only by a unique code.

All sequencing data (large data files) will be processed/stored on platforms maintained by University of Michigan Advanced Research Computing (<https://arc.umich.edu/systems-services>), which is part of UM Information and Technology Services. Specifically, we will store coded data

(no HIPAA identifiers) on Turbo and utilize the Great Lakes high-performance cluster to process the raw sequence data and perform analyses of the metagenomic sequence data. Several of the analysis pipelines to be used are already or can be installed for microbial metagenomic analysis. UM-DropBox (HIPAA-compliant) will be used to store intermediary and final result files that need to be easily accessed for non-computationally intensive analyses, discussions and write-ups by the research team.

XII. Data Analysis

This is a pilot, proof-of-concept study. There is no available published data (at the time of writing) that addresses the same research questions to perform a sample size calculation based on changes in microbiome readouts (primary objective/endpoint) related to dupilumab intervention. However, we have previously reported significant changes in the airway microbiome, related to a prospective treatment intervention (fluticasone propionate), in comparisons that also involved small numbers of subjects. Specifically, in an earlier NHLBI AsthmaNet Proof-of-concept study, we examined the effects of randomized, placebo-controlled fluticasone intervention (6 weeks) on the airway microbiome in subjects with mild asthma. We identified fluticasone-associated changes in the airway microbiome between steroid-responders vs. non-responders, in an initial analysis of paired protected bronchial brushings from 16 subjects [13]. In an analysis of induced sputum from the same study, we recently reported changes in the airway microbiome related to fluticasone intervention, which differed from placebo [14]. Notably, we observed a significantly greater change in airway microbial community structure in ICS non-responders (n=8) compared to responders (n=12).

To address our exploratory hypotheses in this pilot study, we will first generate the following readouts of microbial community composition: (1) read counts or relative abundance data for each microbial species determined from sequence alignments to reference databases. These readouts can be at the level of ASVs (amplicon sequence variant) or OTUs (operational taxonomic unit), which can also be collapsed into higher taxonomic levels for analysis, e.g. genus or family-level comparisons; (2) within-sample and between-sample measures of microbial diversity, i.e. alpha- or beta-diversity. Alpha-diversity measures will include Shannon, inverse Simpson, richness, and the phylogeny-based Faith index. Beta-diversity measures will include calculation of Bray-Curtis and Unifrac distance measures, the latter being a phylogeny-based calculation of between-sample differences in overall microbial composition. We will also determine 16S rRNA gene copy numbers in induced sputum by quantitative PCR, which serves as a proxy measure of 'bacterial burden' often used in the airway/lung microbiome literature. Other generated molecular data will be used to explore secondary questions related to whether dupilumab intervention effects change in predicted microbial functions (KEGG orthologue modules and pathways), intestinal metabolites, and whether changes in the airway or gut microbiome correlate with changes in inflammatory markers and immune mediators measured in sputum, blood and NELF.

For Hypothesis 1, we will compare sputum bacterial burden (normalized 16S rRNA gene copy number) before and after treatment (baseline vs month 1; baseline vs. month 4; all three timepoints), using paired t-test if normally distributed (Wilcoxon sign-rank test if non-normal distribution) and repeated measures ANOVA for all three timepoints.

For Hypothesis 2, we will compare alpha-diversity measures before and after treatment (baseline vs month 1; baseline vs. month 4; all three timepoints), using paired t-test, Wilcoxon sign-rank test or rm-ANOVA. For beta-diversity -based measures of overall microbial composition, we will use Bray-Curtis or Unifrac distance matrices to perform (i) pairwise PERMANOVA tests (R package vegan; adonis2 or in QIIME2 (q2-longitudinal) [20,21]; (ii) linear mixed-effects models with a random intercept and slope for each individual; (iii) Procrustes analysis with Mantel test. We will also explore other available tools for time-series microbiome analysis such as MDSINE [22]. Differences in specific species (ASVs, OTUs) between time points will be analyzed using DESeq2 which applies a variance-stabilizing transformation to the data. Other methods using log-ratio transformation (e.g., CLR) of species counts will also be explored.

For Hypothesis 3, we will examine correlations between change in biomarkers (e.g., cytokines, inflammatory cell counts, targeted gene expression) and changes in the airway or gut microbiome. The latter based on either specific compositional readouts (ASV, OTUs) or in terms of overall microbial community structure. The following approaches will be used: (i) initial correlation analyses performed between paired data at each time point (e.g., specific biomarker dataset vs. microbial ASVs), using Spearman correlations, with adjustments for multiple comparisons by q-values; (ii) linear mixed-effects models, e.g. levels of immune markers as predictors of post-treatment microbiota diversity or abundances of each microbiota member; fixed effects would include age, sex, BMI, and chronic treatments including corticosteroids or macrolides (type, dose, route); (iii) tests for biomarker association with overall microbial community structure, using distance-based PERMANOVA (adonis2) at each time point or in a paired design; (iv) additional computational approaches based on methods for high-dimensional dataset comparisons, as described below.

For Hypothesis 4, which focuses on microbial correlations with clinical outcome measures rather than biomarkers, we will apply same approaches as described for Hypothesis 3. In addition, we will explore the following analysis methods (also applicable to Hypothesis 3): (i) feature-volatility action algorithm, which performs longitudinal feature selection based on random forest regression, implemented in q2-longitudinal in QIIME2; (ii) tools in the R mixOMICS package which bundles access to several sparse multivariate modeling methods that aim to identify key features that explain a biological or clinical outcome of interest.

Related to this, and to leverage tools for examining microbiome data with other -omics/high-dimensional data we will apply tools such as DIABLO (available in mixOMICS package). DIABLO performs data integration coupled with discriminant analysis approach to identify combinatorial features predictive of a binary outcome (e.g., is there a combination of microbial and metabolite features that predict improved asthma control or not? or that associate with an immune biomarker of interest?) As an example, we have recently used DIABLO to explore microbial and metabolite features associated with COPD outcome measures in a multicenter study. In addition, we will determine co-occurrence relationships between microbiota (SparCC [24] or SPIEC-EASI [25]) to identify highly correlated species and determine if 'hubs' of microbiota associate with particular cytokines or metabolites, following by analysis for clustering patterns of microbial-immune relationships [26]. Given the likely heterogeneity of measures in the molecular data types and the small number of subjects, we will apply corrections for multiple comparisons where indicated.

References

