Immune and Other Microbial Biomarkers - blood, induced sputum, nasal epithelial lining fluid (NELF), stool, exhaled air

- Serum total IgE and specific IgE to aeroallergen panel (ImmunoCap)
- Complete blood count with cell differential
- Sputum cell differential counts
- Sputum, NELF cytokines (Mesoscale Discovery; 30-plex panel: Eotaxin, Eotaxin-3, GM-CSF, IFN- γ , IL-10, IL-12/IL-23p40, IL-12p70, IL-13, IL-15, IL-16, IL-17A, IL-1 α , IL-1 β , IL-2, IL-4, IL-5, IL-6, IL-7, IL-8, IL-8 (HA), IP-10, MCP-1, MCP-4, MDC, MIP-1 α , MIP-1 β , TARC, TNF- α , TNF- β , VEGF-A)
- Sputum antimicrobial peptide expression (RT-PCR): defensins, lysozyme, lactoferrin, LL-37, and secretory leukocyte protease inhibitor
- Total bacterial burden in sputum samples by 16S rRNA Q-PCR or droplet digital PCR; with determination of both relative and absolute abundances of taxa.
- Respiratory microbial functional gene annotations from metagenomic sequencing
- Fecal metabolites by global/untargeted and targeted short-chain fatty acid assays

Primary hypotheses:

Hypothesis 1. Dupilumab-induced suppression of T2 inflammation in severe asthma is associated with changes in respiratory tract bacterial burden at 1 month and 4 months after treatment initiation (16S rRNA qPCR of bacterial DNA in induced sputum)

Hypothesis 2. Dupilumab-induced suppression of T2 inflammation in severe asthma is associated with changes in the compositional structure of respiratory and/or gut microbiota, detectable at 1 month and 4 months after initiation of treatment. (bacterial and fungal microbiota profiles and related measures of microbial diversity in induced sputum and stool)

Hypothesis 3. Dupilumab-induced changes in specific biomarkers (e.g. T2 and non-T2-related cytokines; targeted gene expression) correlate with changes in the respiratory and/or gut microbiome (phylogenetic diversity, specific compositional and functional profiles)

Hypothesis 4. Dupilumab-related improvement or lack of improvement in clinical outcomes (lung function, asthma control scores) over a 4-month period are associated with changes in specific characteristics of the respiratory and/or gut microbiome.

IV. STUDY OVERVIEW, INCLUSION/EXCLUSION CRITERIA, PROCEDURES

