Dupilumab-eligible severe asthma patients will be identified and recruited from asthma and allergy clinics at the University of Michigan. Severe asthma patients are seen and cared for by Pulmonary and Allergy faculty at two main outpatient clinic locations. All severe asthma patients who meet clinical prescribing criteria for dupilumab are considered eligible and will be recruited for this study. The study coordinator and/or physician investigator will meet with subjects to provide information about the study and invite them to participate in this 3-visit study occurring over a 4-month period. We will enroll 15 severe asthma patients who complete all 3 visits. The funder of the grant for this project (Regeneron) will provide dupilumab for this study.

Inclusion criteria:

1. Adults ages 18 or older with physician-diagnosed/-managed severe asthma who are clinically eligible for dupilumab (clinical criteria below).
2. Current treatment with a medium-to-high-dose inhaled glucocorticoid (fluticasone propionate at a total daily dose of ≥ 440 μ g or equipotent equivalent) plus up to at least one additional controller (e.g., a long-acting β 2-agonist or leukotriene receptor antagonist)
3. Eosinophilic asthma phenotype (blood eosinophil level >300) or asthma requiring daily oral corticosteroids
4. Asthma that is uncontrolled, as defined by a score on the Asthma Control Test of 19 or lower, OR a worsening of asthma in the past year that led to an asthma hospitalization, ED visit, or 3 days of oral corticosteroids
5. Severity of asthma that, in the opinion of the subject's asthma care specialist, requires dupilumab for control

Exclusion Criteria:

1. Patients with diagnosis of other chronic lung diseases (e.g. COPD, idiopathic pulmonary fibrosis, Churg-Strauss syndrome, ABPA, etc.)

2. Current smoker or reported smoking within 1 month of the screening visit (tobacco or any inhaled recreational product)
3. Greater than 10 total pack-year of cigarette smoking history
4. Treatment with oral corticosteroids for an asthma exacerbation 1 month prior to screening or during the screening period
5. Use of any biologic therapy for asthma within the past 3 months
6. Respiratory or GI illness within 1 month prior to screening or during the screening period
7. Treatment with antibiotics for acute infections within six weeks prior to screening or during the screening period.
8. Pregnancy at enrollment or during the study
9. Known hypersensitivity to dupilumab or its excipients

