Appendix 1. Asthma Control Test (ACT)

The Asthma Control Test (ACT) is a patient self-administered tool for identifying those with poorly controlled asthma. It is based on a 4-week recall of symptoms and daily functioning captured in 5 items on the questionnaire. These include assessment of the frequency of shortness of breath, general asthma symptoms, use of rescue medications, the effect of asthma on daily functioning, and overall self-assessment of asthma control. Each item is scored on a 5-point scale, with higher scale values indicative of, depending on the question, infrequent/absent symptoms or better asthma control.

The ACT score is the sum of the values for all 5 items. The scores range from 5 (poor control of asthma) to 25 (complete control of asthma), with higher scores reflecting greater asthma control.

An ACT score >19 indicates well-controlled asthma; the minimal clinically important difference in score is 3.

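### Change in ACT is bounded by the Visit 1 score, which inclusion criterion 4 leaves open at the top, and the Hypothesis 4 models do not adjust for it

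*Combined protocol and SAP*

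**What the plan says.** Inclusion criterion 4 in Section IV has two routes. The first is "Asthma that is uncontrolled, as defined by a score on the Asthma Control Test of 19 or lower". The second is "OR a worsening of asthma in the past year that led to an asthma hospitalization, ED visit, or 3 days of oral corticosteroids". Either is enough. Criterion 5 adds a specialist's judgement, "Severity of asthma that, in the opinion of the subject's asthma care specialist, requires dupilumab for control", with no ACT value attached. Exclusion criterion 4 bars "Treatment with oral corticosteroids for an asthma exacerbation 1 month prior to screening or during the screening period".

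Appendix 1 describes the ACT as running from 5 to 25. On recall it says: "It is based on a 4-week recall of symptoms and daily functioning". On interpretation it says: "An ACT score >19 indicates well-controlled asthma; the minimal clinically important difference in score is 3".

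Hypothesis 4 in Section III concerns "Dupilumab-related improvement or lack of improvement in clinical outcomes (lung function, asthma control scores) over a 4-month period" and its association with changes in the microbiome. The third secondary objective asks whether immune markers and microbiota patterns together predict who improves clinically and who does not. Section XII gives Hypothesis 4 the same methods as Hypothesis 3: Spearman correlations, mixed-effects models and PERMANOVA. The fixed effects named there are age, sex, BMI and long-term treatments. Section XII also offers, as an example for the DIABLO method, a search for features that "predict improved asthma control or not". No section says what counts as improvement, and none says how the starting ACT score is handled.

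**The concern.** A patient can satisfy the criterion for uncontrolled asthma through an event some months old and still have a Visit 1 ACT in the range that Appendix 1 calls well controlled. Such a patient has little or no room to improve on the scale. If ACT change is analysed without reference to where each patient started, part of its variation is simply distance from the ceiling.

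Any microbial or immune feature that tracks the level of control at Visit 1 can then appear to be linked to response or non-response to dupilumab. The risk is clearest for the third secondary objective, which is about prediction. It also reaches Hypothesis 4 if a change in the microbiome is itself related to starting control. With 15 patients, a few near the ceiling could shape the result.

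**Working it through.** **Inputs.** ACT: 5 items, each on a 5-point scale; range 5 to 25; above 19 is well controlled; minimal important difference 3; recall 4 weeks (Appendix 1). Entry rules: Section IV. Visit timing: Table 1. Sample: 15 completers (Section IV). Covariates: Section XII. The documents give no distribution of Visit 1 ACT.

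**1. Reproduce the scale.** Taking items as scored 1 to 5, the minimum is 5 × 1 = 5 and the maximum is 5 × 5 = 25, as stated.

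**2. Largest possible gain = 25 − Visit 1 ACT.**

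| Visit 1 ACT | Largest gain | Above 19? | Can gain 3? |
|---|---|---|---|
| 19 | 6 | no | yes |
| 20 | 5 | yes | yes |
| 21 | 4 | yes | yes |
| 22 | 3 | yes | yes |
| 23 | 2 | yes | no |
| 24 | 1 | yes | no |
| 25 | 0 | yes | no |

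Since 25 − 3 = 22, the scores that cannot rise by 3 are exactly 23, 24 and 25.

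**3. Can such scores occur?** Visit 1 is 2 to 4 weeks after screening, so its 4-week recall window opens between 2 weeks before screening and the day of screening (2 − 4 = −2; 4 − 4 = 0). Exclusion 4 covers the month before screening and the screening period. If that period runs up to Visit 1, the whole window is free of exacerbations treated with oral corticosteroids, while the qualifying event may be up to a year old. High scores are therefore possible. How common they are cannot be derived.

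**4. Effect under each outcome definition built on the Appendix 1 figures.**
- *Rise of 3 or more:* patients at 23 to 25 cannot qualify. With k of them among 15, the largest attainable improver rate is (15 − k)/15: 93.3% for k = 1, 86.7% for k = 2, 80.0% for k = 3.
- *Month-4 ACT above 19:* a patient already above 19 can count as improved with no change.
- *Continuous change:* no one is forced into a class, but the upper bound on gain is 0 to 2 points at 23 to 25 and at least 6 at 19 or lower.

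Under all three, the outcome partly encodes the Visit 1 score, and the named covariates do not include it.

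**5. How many patients? Assumptions only.** If a share q of eligible patients scores 23 to 25, the expected number is 15q and the chance of at least one is 1 − (1 − q)^15:

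| q (assumed) | Expected of 15 | Chance of at least one |
|---|---|---|
| 0% | 0 | 0% |
| 5% | 0.75 | 54% |
| 10% | 1.5 | 79% |
| 20% | 3.0 | 96.5% |
| 30% | 4.5 | 99.5% |

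Under a 3-point rule, and assuming that 40% of the other patients do not improve, ceiling cases make up k/(k + 0.4(15 − k)) of the non-improvers: 0% for k = 0, 1/6.6 = 15% for k = 1, 3/7.8 = 38% for k = 3. For k = 3, replacing 40% by 20% or 60% gives 3/5.4 = 56% or 3/10.2 = 29%.

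**The case against.** The strongest reply is that the plan commits to no responder rule. The 3-point figure appears only in the appendix describing the instrument and is tied to no analysis, and the yes/no outcome in Section XII is an example. This stands. A reader might infer that patients at 23 to 25 will automatically be classed as non-improvers; the documents do not support that, because the result follows only if a 3-point rise is chosen.

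Second, admitting patients on exacerbation history is a legitimate way to recognise uncontrolled severe asthma, and criteria 1 to 3 and 5 make very high ACT scores less likely. This also stands. Criterion 4 is not an error, and the share near the ceiling may be small. But none of these criteria caps ACT, so the possibility remains.

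Third, Hypothesis 4 concerns changes in the microbiome, so a baseline marker of good control would not enter it directly. That is fair, and it narrows the most direct harm to the third secondary objective and the analyses at single time points. It does not remove the dependence of ACT change on the starting score, which affects any association with ACT change.

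Fourth, Visit 1 ACT is collected anyway, and the mixed-model covariate list is part of an illustrative description, so the analyst could adjust without a change to the plan. True, but nothing written says so.

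Finally, limiting the ACT analyses to 19 or lower would also discard patients at 20 to 22, who can still gain 3 points. With 15 patients that is a real loss, so the restriction belongs in a sensitivity analysis.

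**Conclusion.** The point holds in a limited form. Criterion 4 leaves Visit 1 ACT open at the top, the possible gain in ACT depends on that score, and the covariates named for the Hypothesis 4 models leave it out. The headroom figures are exact. The classification problem at 23 to 25 is conditional on a 3-point rule that the plan does not adopt. The number of patients concerned is unknown and could be zero; the shares and percentages in the working rest on assumed values of q, k and the true non-improvement rate.

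The reach is narrow. Hypothesis 4 is listed among the primary hypotheses, but Section XII calls the hypotheses exploratory and the study a pilot. The microbiome endpoints do not use ACT, and lung function, the other outcome named in Hypothesis 4, is untouched by the ACT ceiling. A reader might take the point as a reason to change who is admitted or to doubt the primary endpoints; neither follows.

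**What to change.** In Section XII, for Hypothesis 4 and the third secondary objective:

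- Include Visit 1 ACT as a covariate in every model of ACT change. For the correlation analyses, use partial Spearman correlation given Visit 1 ACT.
- Name baseline-adjusted continuous ACT change as the main ACT outcome.
- If a binary rise of 3 or more is also used, for example in DIABLO, state that rule, leave out only patients with Visit 1 ACT of 23 to 25, report how many there were, and add a sensitivity analysis limited to 19 or lower.

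Entry criteria stay as they are, and all patients remain in every other analysis.

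The cost is wording plus one degree of freedom in small models: counting long-term treatments as one term, the four named covariates become five. The binary analysis alone loses patients, and only those who could not have met its definition. Adjustment takes out the average dependence on the starting score; it cannot recover improvement that the scale is unable to record at its ceiling.

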Study Title: Effects of Interleukin (IL)- 4R-alpha Inhibition on Respiratory Microbiome and Immunologic Correlates in Severe Asthma

PI: [name]

NCT: NCT05036733

Protocol Version IRB Approval Date: 9/8/2021

Effects of IL-4 α Inhibition On The Respiratory Microbiome And Immunologic Correlates In Patients With Severe Asthma: A Pilot Study

Principal Investigator: [name]; UM Division of Pulmonary/Critical Care Med

Co-Principal Investigator: [name] MD; UM Division of Allergy/Clinical Immunology

Co-Investigator: [name]; UM Division of Pulmonary/Critical Care Med

I. Overview

This prospective pilot study will address the following main research question: *“Does IL-4Ra (dupilumab) inhibition of Type 2-mediated immune responses alter the respiratory microbiome within a 4 month period of treatment initiation and follow up, and if so, what are the specific microbiological changes and immune response correlates of these changes?”* We will compare pre- and post-dupilumab effects on the microbiomes, immune responses and metabolome of severe asthma patients who are clinically eligible for dupilumab treatment. Eligible patients will be screened and enrolled prior to start of therapy and return for visits at 1 month and 4 months after initiation of treatment. The overall goal of this study is to understand biological responses related to dupilumab treatment among severe asthma patients who have clinical indication to be treated. We will collect biospecimens (nasal, sputum, stool, blood) to examine dupilumab-related changes in the microbiome, measured immune responses, and clinical outcome measures. Research methods will include microbiome profiling of respiratory and stool samples, cytokine measurements from nasal epithelial lining fluid, and metabolite analysis of stool samples.

II. Background

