2 Per current policy (as of Jan 2021) at Michigan Medicine, subjects must undergo COVID-19 testing (nasal swab) and have a negative test within 96 hrs prior to aerosol-generating procedures. Testing will be arranged by study team for each visit. If the test is positive for COVID-19 or test result is not available, the study visit will need to be rescheduled.

3 A physician must see the subject at each visit.

4 FeNO measurement and NELF collection should be performed before spirometry and sputum induction.

5 Brief telephone call by study coordinator to (a) ensure subjects are self-administering dupilumab doses between study visits, (b) address any interim questions, and (c) remind them of upcoming in-person study visit. The TC encounters are important to maintain contact with subjects and ensure adherence and follow through during the course of the study

V. VISIT-SPECIFIC DETAILS

SCREENING.

This is the first encounter with eligible patient at which time information about the study is provided by the study coordinator. This may occur by phone or email. A short list of questions will be asked to confirm eligibility. If on the basis of this screen, an individual is eligible to participate the study, a copy of the informed consent will be provided for subject review prior to Visit 1. Signed informed consent will be collected at Visit 1. (*Anticipated total time by study coordinator: 10 minutes.*)

VISIT 1.

Preparations

1. V1 should be scheduled within 2-4 weeks after screening. Subjects will be reminded by study coordinator to take their usual asthma treatments as prescribed including on the day of the visit. Coordinate V1 scheduling with physician investigator availability to perform history and physical exam.
2. Coordinate with Research Pharmacy preparation of dupilumab syringe for administration to subjects after completing all visit testing. Ensure appropriate orders are submitted in advance of V1 date. Also ensure subject will have subsequent doses of dupilimab prepared for self-administration at home between V1 and V2.
3. Notify [name] in [name] Lab ([name]) the day before the visit so that the lab can prepare necessary materials to collect and process samples. Ensure a bucket of ice is available to place collected samples for transport to [name] lab.

Visit procedures

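### Exclusion 4 bars only oral corticosteroids given for an asthma exacerbation, so patients with other recent systemic steroid exposure can enter with no written washout before the single baseline sample

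*Combined protocol and SAP*

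**What the plan says.** Section IV has one exclusion that names corticosteroids, item 4: "Treatment with oral corticosteroids for an asthma exacerbation 1 month prior to screening or during the screening period". Items 5 and 7 cover biologics and antibiotics. Item 6 is the nearest criterion that could remove other steroid users, and it works through the illness rather than the drug: "Respiratory or GI illness within 1 month prior to screening or during the screening period".

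Daily oral corticosteroid is deliberately allowed. Inclusion 3 reads "Eosinophilic asthma phenotype (blood eosinophil level >300) or asthma requiring daily oral corticosteroids", without a date for the count. Inclusion 4 can be met by "a worsening of asthma in the past year that led to an asthma hospitalization, ED visit, or 3 days of oral corticosteroids".

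On timing, Section V states that "V1 should be scheduled within 2-4 weeks after screening". Baseline specimens are taken at Visit 1, just before the first dose. The design is a within-patient comparison: "We will compare pre- and post-dupilumab effects on the microbiomes, immune responses and metabolome of severe asthma patients".

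In Section XII, Hypothesis 1 and the alpha-diversity part of Hypothesis 2 use paired t-tests, Wilcoxon tests or repeated-measures ANOVA without covariates. Steroid adjustment appears only in the mixed models for Hypothesis 3, carried over to Hypothesis 4, and only for "chronic treatments including corticosteroids or macrolides (type, dose, route". The same section cites the study team's own published sputum data from a fluticasone trial, which showed "changes in the airway microbiome related to fluticasone intervention, which differed from placebo".

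**The concern.** The protocol accepts that recent steroid treatment should be kept away from the baseline, since it imposes a washout, but it applies that washout to one route and one indication. Nothing in the documents explains why an injection, or an oral course for a skin condition, should be treated differently.

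The Visit 1 sample is each patient's only comparator. If a short course is wearing off at that visit, recovery coincides with the start of dupilumab and the paired tests cannot separate the two. The covariate for chronic treatment would not pick up a short course. The medication item among the clinical outcomes in Section III covers asthma medication, so a course given for another reason may not be recorded, and an unrecorded exposure cannot be adjusted for afterwards.

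**Working it through.** The plan states no alpha, power, effect size or SD, so there is no figure to reproduce. The check has three parts.

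**1. Written washout at Visit 1.** Take one month as 30 days and Visit 1 at 14 to 28 days after screening.
- Oral course for an asthma exacerbation: barred in the month before screening and during screening, so at least 30 + 14 = 44 to 30 + 28 = 58 days, depending on when Visit 1 falls.
- Injected steroid, or an oral course for another reason, where Exclusion 6 does not apply: no criterion bars it before or during screening, so the written minimum is 0 days.

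**2. Effect on a paired test.** Assumptions, none from the documents except n = 15: paired changes are normal with SD 1; k patients have a baseline displaced by s, which shifts their change by s; the test is a two-sided one-sample t-test on the changes at 0.05.

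Bias in the mean change = k × s / 15. For s = 0.8 and 1.2:
- k = 1: 0.8/15 = 0.05; 1.2/15 = 0.08
- k = 2: 1.6/15 = 0.11; 2.4/15 = 0.16
- k = 3: 2.4/15 = 0.16; 3.6/15 = 0.24

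Simulated rejection rates over the same range of s:

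| Affected (k) | Bias, SD of change | Type I error, no true change | Power, true change 0.8 SD, shift opposing it |
|---|---|---|---|
| 0 | 0 | 5% | 0.82 |
| 1 | 0.05-0.08 | 5% | 0.71-0.75 |
| 2 | 0.11-0.16 | 6-7% | 0.57-0.68 |
| 3 | 0.16-0.24 | 7-10% | 0.43-0.59 |

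The power column describes any endpoint tested this way. It is not the power of a planned test of the fall in Type 2 (T2) markers, because Section XII specifies no stand-alone test of that.

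**3. How many could be affected.** The documents give no prevalence. If a proportion p of eligible patients were exposed, the chance of at least one in 15 is 1 − (1 − p)^15; the other columns are the matching binomial tails.

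| p (assumed) | 1 or more | 2 or more | 3 or more |
|---|---|---|---|
| 5% | 54% | 17% | 4% |
| 10% | 79% | 45% | 18% |
| 20% | 97% | 83% | 60% |

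**Direction.** Section II reports lower airway bacterial burden where T2 inflammation is higher. On that reasoning, T2 recovery after a steroid would push burden down, while T2 suppression by dupilumab would push it up. The two oppose each other, which points to masking. This holds only if the steroid acts on burden through T2 inflammation, and the documents do not establish that.

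**The case against.** The gap is narrower than the wording of Exclusion 4 alone suggests. Section IX groups sinusitis with upper respiratory infections as intercurrent illness, so a recent course for sinusitis plausibly falls under Exclusion 6. So does an injection at a recent emergency visit for asthma, on an ordinary reading of respiratory illness. Inclusion 4 looks back a year and does not by itself point to recent exposure. Visit 1 comes 2 to 4 weeks after screening, so a course finished before screening is at least 14 days old at baseline. Eligibility is reviewed again at Visit 1, with a full history. The eosinophil threshold would remove some suppressed patients if the count was taken after the steroid.

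These points stand, and they reduce how many patients the gap lets through. They do not close it. Exclusion 6 leaves skin, joint and allergic indications open, and injections for them. Nothing bars such a course during screening itself. Reviewing criteria again does not help if they do not ask the question. The eosinophil count is undated, and the daily oral steroid route bypasses it.

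The cited fluticasone study is indirect: six weeks of inhaled drug in mild asthma, whereas everyone here already takes a medium-to-high inhaled dose. It makes an effect plausible but does not measure carry-over from a short systemic course.

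Two stronger readings are tempting. A reader might infer that an exposed patient necessarily enters with a suppressed, recovering baseline; the documents give no size or duration of carry-over, so the supportable statement is that such a patient can enter. A reader might also infer that a rebound would be reported as a drug-related microbiome change. The burden finding in Section II makes masking or noise likelier, and the type I error inflation assumes no drug effect and is absent with one affected patient.

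**Conclusion.** The gap is real and no other section closes it: systemic corticosteroid exposure outside Exclusion 4's route and indication, and not caught by Exclusion 6, has no written washout. It matters because the baseline is a single sample, there is no control arm, and the Hypothesis 1 and 2 tests cannot adjust for it. The likelier consequence is added noise or a masked change in a 15-patient study; bias in the other direction cannot be excluded.

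The sizes in the tables rest on assumed shifts and assumed numbers affected. With one such patient the bias is below 0.1 SD and type I error is unchanged; with three, the effect on power is substantial. Patients on stable daily oral corticosteroid are admitted on purpose and are not the issue here. For an exploratory pilot this should be corrected because it is cheap to do so. It does not invalidate the design.

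**What to change.** - **Eligibility.** Extend Exclusion 4, keeping its existing window, to any non-maintenance systemic corticosteroid regardless of route or indication. State that stable daily oral corticosteroid under Inclusion 3 is not an exclusion. The investigators should also state how a temporary increase above the daily dose counts for eligibility, since otherwise that case stays ambiguous.
- **Ascertainment.** Add the question to the screening list and to the Visit 1 eligibility review.
- **Recording.** Record all systemic corticosteroid exposure before Visit 1 by route, indication and date, including courses given for reasons other than asthma.
- **Analysis.** Pre-specify a sensitivity analysis of Hypotheses 1 to 3 without exposed patients. If eligibility is not widened, recording and this analysis are the minimum.

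The cost is one sentence in the criteria, one screening question and a short data-entry item. The downside is that a few patients wait until they are outside the window and are re-screened, which slows recruitment slightly. A sensitivity analysis that drops patients from 15 will be imprecise and should be read for consistency of the estimate, not for significance.
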